10.2 Lost-to-follow-up, dropouts and subgroup analysis

Refer to § 19.1 for lost-to-follow-up procedure.

¹ LCP performance includes capture thresholds, R-wave amplitude, battery voltage and pacing impedance.

Investigator will provide data on subjects, in whom an implant was attempted but who were unable to have a device implanted, to record and report any SAEs during and up to 30 days from the attempt.

Reasons for inability to implant the LCP device include, but are not limited to, tortuous anatomy not allowing passage of the LCP, inability to advance introducer into the femoral vein or straight portion of the inferior vena cava, or vessel size not allowing insertion of 18F introducer. Subjects who are enrolled but never undergo an implant attempt will be followed for 30 days post attempt by the Investigator and will be reported by the Sponsor.

10.3 Termination on statistical grounds

Criteria for terminating the clinical study on statistical grounds are not needed because this is a study of a CE-marked device within its intended use, for which existing vigilance regulations and procedures provide adequate safeguards.

At any time, any subject may terminate his or her participation as provided in their informed consent, and any investigator may terminate his or her participation as provided in their investigator agreement.

11 DATA MANAGEMENT

Data collected through an EDC system or paper case report forms will be available in a central database. Sponsor will review all incoming data to identify inconsistent or missing data as well as any adverse events. Sponsor will promptly address any data issues with the Investigator. Sponsor will establish quality assurance procedures to ensure that complete, accurate and timely data are submitted, that observational study plan requirements are followed and that complications, adverse events and adverse device effects are correctly reported and investigated, as appropriate. Investigator will maintain all source documents as required by the observational study plan, including laboratory results, supporting medical records, and signed Informed Consent forms. Sponsor and/or monitor will use source documents during the regular monitoring visits to verify information from the database against data contained on the completed CRFs.

11.1 Data retention

Sponsor and Investigator will maintain the clinical investigation documents for a minimal period of five (5) years after the clinical investigation is completed, or longer depending on national requirements. They will take measures to prevent accidental or premature destruction of these documents and ensure these

are filed in a secure place. Investigator or Sponsor may transfer custody of records to another person or party and document the transfer at the investigation site, or at the Sponsor's facility.

11.2 Clinical quality assurance and quality control

Sponsor has integrated clinical quality assurance and quality control in the Sponsor's quality system. Quality assurance and quality control principles will apply to the processes of the clinical study. Sponsor will:

- Implement and maintain written clinical quality procedures to ensure that the clinical study is designed, conducted and monitored, and that data are generated, documented, recorded and reported in compliance with ISO 14155:2011, the observational study plan, any subsequent amendment(s), and any other applicable standards and regulatory requirements,
- Maintain records to document the compliance of all parties involved in the clinical study,
- Ensure that the auditing requirements are met, and
- Justify and document significant exceptions to the requirements of ISO 14155:2011.

12 AMENDMENTS TO AND DEVIATIONS FROM THE OBSERVATIONAL STUDY PLAN

Sponsor and Investigator will conduct this clinical investigation in accordance with the Observational Study plan, ISO 14155, and all applicable regulatory requirements associated with the Active Implantable Medical Device Directive, including transpositions of the Directive into national law.

Investigator will not deviate from the Observational Study plan without prior written confirmation by Sponsor, or their designee, except as required in a medical emergency. In medical emergencies, Sponsor does not require prior confirmation for protocol deviations, but Investigator will notify Sponsor within 5 days of the incident and will notify the EC according to local requirements. Investigator, or designee, will record deviations with an explanation for the deviation. Investigator will report to Sponsor who will analyze them and assess their significance.

Routine monitoring will assess Investigator compliance to the protocol as described in §9.5.

Investigator must not modify the Observational Study plan without the prior and written permission from Sponsor. Sponsor and Investigator will agree to all amendments made to the Observational Study plan. Sponsor and/or Investigator will record a justification for the amendments. If Observational Study plan changes affect the scientific soundness of the clinical investigation, or affect the health, welfare, safety and rights of subjects, Investigator and/or Sponsor will obtain written approval by the Investigator's EC, and Competent Authority, when applicable, before implementing changes. If changes are merely administrative in nature, Investigator will notify their EC.

13 DEVICE ACCOUNTABILITY

This is an observational study to confirm positive benefit/risk balance in a CE-marked device within its intended use; consequently it does not require special device accountability procedures for the post-market clinical study. The manufacturer's standard operating procedures for shipping and receiving will suffice.

14 STATEMENTS OF COMPLIANCE

1. Sponsor and Investigator will conduct the clinical study in accordance with the ethical principles that have their origin in the Declaration of Helsinki.
2. Sponsor and Investigator will comply with applicable parts of ISO 14155:2011 and any regional or national regulations, as appropriate.
3. Investigator will not begin the clinic study until Investigator obtains the required written approval or favorable opinion from the EC or regulatory authority, if appropriate.
4. Investigator will follow any additional requirements imposed by the EC or regulatory authority, if appropriate.
5. Sponsor will provide insurance for subjects.

15 INFORMED CONSENT PROCESS

Investigators will not ask subjects to sign the Informed Consent Form (ICF) until the clinical study has been fully approved by the institution's EC, and the Sponsor or their CRO representative has received and reviewed the specific EC-approved ICF. When Investigator has determined the eligibility of a specific subject to enter the clinical study, Investigator, or designee, will discuss and explain the clinical investigation with the subject. Investigator will provide ICF to the subject. Subject will read the ICF, and Investigator will answer any questions. Investigator will provide ample time to the subject to decide on his/her participation and obtain a signed ICF from the subject before performing the implant procedure or any protocol-specific tests. Investigator will provide subjects with a copy of their signed ICF. Investigator will provide new information to new and existing subjects.

Investigator will maintain a copy of the EC-approved ICF along with a copy of each subject's signed Informed Consent Form in a designated study file.

16 ADVERSE EVENTS, ADVERSE DEVICE EFFECTS AND DEVICE DEFICIENCIES

Using the specific signs, symptoms or abnormal laboratory values, Investigator will classify and report adverse events. Investigator will use medical diagnosis if no signs, symptoms or abnormal laboratory values are identified. A Clinical Event Committee (CEC) will adjudicate all device or procedure-related adverse events in the study.

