8 OBJECTIVES OF THE OBSERVATIONAL STUDY

This clinical study will confirm the clinical performance and safety of the Nanostim LCP system for subjects who are indicated for a VVI(R) pacemaker by following 1000 patients for 5 years. The primary PMCF requirement for this study will be the complication-free rate at 180 days for 300 patients. Complications are defined as serious adverse device effects (SADE).

Sponsor will record and report pacing, sensing, and other performance endpoints listed in §9.1.2. Sponsor will also assess residual risks identified in the risk analysis section, and incidence of anticipated adverse events and adverse device effects listed in Table , §16.8.

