16.8 List of foreseeable adverse events and anticipated adverse device effects

The table below provides a list (non-exhaustive) of potential adverse events, device related, procedure related and/or subject condition related.

-Next Page-

Table 3: List of foreseeable adverse events and anticipated adverse device effects

Air embolism	Interruption of desired pacemaker function due to electrical interference, either electromyogenic or electromagnetic
Angina pectoris	Keloid formation
Arterial puncture	Loss of normal device function due to battery failure or component malfunction
Bladder puncture	Muscle and nerve stimulation
Blunted or poor sensor response	Myocardial damage
Body rejection phenomena	Myocardial infarction
Bowel penetration	Myocardial irritability
Cardiac arrhythmias	Oversensing
Cardiac dissection	Pacemaker syndrome
Cardiac perforation	Palpitations
Cardiac tamponade	Pericardial effusion
Chronic nerve damage	Pericardial rub
Damage to vessels	Pericarditis
Device dislodgment	Phrenic nerve/diaphragm muscle stimulation
Dizziness	Premature battery depletion
	Programmer/software anomaly
Dyspnea	Pseudoaneurysm formation
Embolism	Psoas abscess
Endocarditis	
Excessive Bleeding	Septic arthritis
Exit block	Seroma
Failure to capture/loss of capture	Syncope
Femoral nerve injury with resulting paresthesias	Threshold elevation
Fluid accumulation	Thromboemboli
Hematoma formation, including retroperitoneal hematoma/hemorrhage	Thrombosis
High impedance	Undersensing
Inability to interrogate or program due to programmer or device malfunction	Valve damage
Induced ventricular ectopy or arrhythmias	Venous occlusion
Infection, local at access site, or system	Venous perforation
Insufficient cardiac output	Ventricular ectopy
Intermittent capture	Ventricular tachycardia

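### Section 16 makes the diagnosis a fallback to signs and symptoms, so the incidences of the Table 3 events come out too low for diagnoses and too high for symptoms

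*Combined protocol and SAP*

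**What the plan says.** The opening paragraph of section 16 sets the order in two sentences. The first is "Using the specific signs, symptoms or abnormal laboratory values, Investigator will classify and report adverse events". The second is "Investigator will use medical diagnosis if no signs, symptoms or abnormal laboratory values are identified". The next sentence gives the committee's remit: "A Clinical Event Committee (CEC) will adjudicate all device or procedure-related adverse events in the study".

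Section 8 commits the sponsor to assessing the "incidence of anticipated adverse events and adverse device effects" set out in section 16.8. That section introduces its Table 3 as follows: "The table below provides a list (non-exhaustive) of potential adverse events, device related, procedure related and/or subject condition related". The table has entries at two levels. Some are diagnoses or device problems, such as "Cardiac perforation", "Device dislodgment", "Failure to capture/loss of capture" and cardiac tamponade. Others are symptoms that such problems produce, such as dizziness, dyspnea, palpitations and syncope.

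The primary endpoint (section 9.1.2) is freedom from serious adverse device effects (SADEs) at 180 days. Freedom from SADEs at 90 days and at 5 years is supplementary.

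**The concern.** The usual order for event terms is the reverse: report the unifying diagnosis when there is one, and fall back on signs and symptoms when there is not. Under section 16 the diagnosis becomes the term only when nothing else has been found, which will seldom be so for a serious complication.

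What is at stake first is the event-specific safety reporting. A post-market study of a new device is read for how often it perforates, dislodges or loses capture. If symptomatic cases are filed under their symptoms, the tables understate those rates. They also show symptom rates that mix device failures with unrelated illness. Because the study objective includes detecting emerging risks, a device problem spread over generic symptom terms is also harder to see.

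The second, weaker stake is the route by which an event reaches the endpoint count, since the committee's remit depends on a prior judgement that the event is related.

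**Working it through.** The plan states no figure on this point, so there is none to reproduce. The check is a comparison of sections, followed by a count in symbols.

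1. **Does the rule govern the event category, or only the narrative?** Section 16 speaks of classifying as well as reporting, so it reaches the category under which an event is counted.

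2. **Does another section reverse the order?** No.
   - Section 16.9 lists the minimum content of the Adverse Event Form: description, onset, severity, relationship, interventions, duration and outcome. It names no field for diagnosis or underlying cause.
   - Section 16.9 also makes the sponsor responsible for classification, but gives no rule for turning symptom terms into diagnoses.
   - The CEC sentence in section 16 does not say that the committee replaces the reported term.

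3. **Which events are affected?** Those with at least one sign, symptom or abnormal laboratory value. A silent dislodgment found at a device check would still be entered under its own name.

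4. **Effect on the Table 3 incidences.** Let N be the true number of events of one diagnosis, s the share with signs or symptoms, and k the number of signs per symptomatic event. Under the rule as written:
   - records under the diagnosis = N × (1 − s), where the correct count is N;
   - extra records under symptom terms = N × s × k, where the correct number is 0.

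   The documents give none of N, s or k. As s runs from 0 to 1, the diagnosis count runs from N down to 0. If one assumes k = 2 to 3 for a tamponade, a single event produces 2 to 3 symptom records and no record under tamponade. The direction is fixed by the rule; the size is not.

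5. **Effect on the SADE endpoints.** Take the same tamponade, entered as 2 to 3 symptom records that are serious and judged device-related. The subject has had a SADE, so the endpoint counts one subject with a complication, exactly as it would under the correct term. The label alone changes nothing. The endpoint changes only if the site also judges the symptom unrelated to both device and procedure. Such an entry is not a SADE and lies outside the committee's stated remit, so no adjudication step is described that would correct it. The documents give no rate for that misjudgement.

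**The case against.** The strongest reply is that the plan has several other routes to the diagnosis.

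- The event form carries a free description, the relationship to device or procedure and the interventions needed, and investigators are to make every effort to supply source documents (section 16.9).
- Table 1 provides separate Device Deficiency, System Revision, Out Of Service and Death forms.
- Threshold, R-wave, impedance and battery voltage are checked from pre-discharge onward (sections 9.4.3 to 9.4.8).
- Section 16.1 counts a new condition, or an abnormal diagnostic result that accompanies symptoms, as an adverse event in itself. An effusion on imaging or loss of capture at a device check could therefore be reported as a finding.
- Because Table 3 contains diagnoses, its authors may have expected diagnosis-level reporting.

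Much of this stands. It would be wrong to say that the diagnosis leaves no trace in the database. What remains is that recovery is possible but not prescribed: no section says who recodes, from which source, or which term enters the tables.

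A reader might also infer that the rule inflates the 180-day and 5-year complication-free rates. The documents do not support that. Sections 16.3 and 16.4 define a SADE by device-relatedness and serious consequences, and add marked loss of device function even when nobody intervenes. No section says that relatedness is judged on the entered term, and an investigator who has treated a tamponade or revised a device will know the cause when recording the relationship. Any figure for the inflation would need an assumed SADE rate and an assumed rate of misattribution, and the documents give a basis for neither.

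**Conclusion.** The point holds for the event-specific incidences. Section 16 states a rule, no other section overrides it, and following it gives Table 3 incidences that are biased downward for diagnoses and upward for symptoms, with single events possibly split over several records. This rests on two assumptions: that sites follow the rule as written, and that no unstated recoding is applied before the tables are made. The size cannot be obtained from the documents.

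For the primary and supplementary SADE endpoints the point is limited to an indirect risk: a symptom entry that the site judges unrelated does not come within the committee's stated remit. A claim that the complication-free rate is overstated by some number of percentage points would go beyond the evidence.

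**What to change.** Reverse the order in section 16, for example: *The event term is the diagnosis or the underlying device or procedure problem when it is known. Signs, symptoms and laboratory values are recorded as its manifestations on the same form, and are reported as separate events only when no diagnosis can be made. If a diagnosis is established later, the term and its relatedness are updated.*

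Add that the existing CEC confirms the term used in the endpoint tables for the events it adjudicates. This needs no wider remit. Updating relatedness when a diagnosis emerges brings a late-recognised device or procedure event within the present one.

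The cost is a short text change, a form-completion guideline for sites, and a one-off query of events already entered under a symptom. The query should be finished before the event tables are produced.

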16.1 Adverse events (AE)

An **adverse event** is any untoward medical occurrence, unintended disease or injury, or untoward clinical signs (including abnormal laboratory findings) in subjects, users or other persons, whether or not related to the investigational medical device.

- This definition includes events related to the investigational medical device.
- This definition includes events related to the procedures involved.
- For users or other persons, this definition is restricted to events related to investigational devices.

A new condition or the worsening of a pre-existing condition will be considered an AE. Stable chronic conditions, such as atrial fibrillation that are present prior to study entry and do not worsen during the clinical investigation will not be considered an AE. An abnormal result of diagnostic procedures including abnormal laboratory findings will be considered an AE if it:

- Results in subject's withdrawal from the clinical investigation by the Investigator;
- Is associated with a serious adverse event;
- Is associated with clinical signs or symptoms;
- Is considered by the physician to be of clinical significance or resulting in a serious deterioration in subject health status.

16.2 Serious adverse events (SAE)

A **serious** adverse event is an adverse event that:

- a. Led to death,
- b. Led to serious deterioration in the health of the subject, that either resulted in
 1. A life-threatening illness or injury, or
 2. A permanent impairment of a body structure or a body function, or
 3. In-patient or prolonged hospitalization, or
 4. Medical or surgical intervention to prevent life-threatening illness or injury or permanent impairment to a body structure or a body function, or
 5. Malignant Tumor
- c. Led to fetal distress, fetal death or a congenital abnormality or birth defect.

NOTE: Planned hospitalization for a pre-existing condition, or a procedure required by the observational study plan, without serious deterioration in health, is not considered a serious adverse event.

Sponsor understands that medical interventions may involve IV and IM drug delivery and surgical interventions involve an invasive procedure. Non-invasive means such as oral drugs or device re-programming do not meet the criteria for medical or surgical intervention.

16.3 Adverse device effect (ADE)

An **adverse device effect** is an adverse event related to the use of a study medical device.

This definition includes adverse events resulting from insufficient or inadequate instructions for use, deployment, implantation, installation, or operation, or any malfunction of the investigational medical device.

This definition includes any event resulting from use error or from intentional misuse of the study medical device.

16.4 Serious adverse device effect (SADE)

A **serious adverse device effect** is an adverse device effect that has resulted in any of the consequences characteristic of a serious adverse event. SADE will include significant loss of device function even if the Investigator chooses not to intervene to correct it.

16.5 Anticipated serious adverse device effect (ASADE)

Anticipated serious adverse device effect is a serious adverse device effect which by its nature, incidence, severity or outcome has been identified in the risk analysis report.

16.6 Unanticipated serious adverse device effect (USADE)

An **unanticipated serious adverse device effect** is a serious adverse device effect, which by its nature, incidence, severity or outcome has not been identified in the current version of the risk analysis report.

16.7 Device deficiency

A **device deficiency** is an inadequacy of a medical device with respect to its identity, quality, durability, reliability, safety or performance. Device deficiencies include malfunctions, use errors, and inadequate labeling.

If a device deficiency is detected or suspected, Investigator will document it on the Device Deficiency Form and return the device according to the instructions provided in the Investigator's study binder(s).

Investigator will report device deficiencies that did not lead to an adverse event but could have led to a medical occurrence:

- a. If either suitable action had not been taken,
- b. If intervention had not been made, or
- c. If circumstances had been less fortunate.

A **malfunction** is a failure of a study medical device to perform in accordance with its intended purpose when used in accordance with the IFU or CIP.

A **use error** is an act or omission of an act that results in a different medical device response than intended by the manufacturer or expected by the user.

Use error includes slips, lapses, and mistakes. An unexpected physiological response of the subject does not in itself constitute a use error.

Refer to reporting requirements in §16.9.

16.8 List of foreseeable adverse events and anticipated adverse device effects

The table below provides a list (non-exhaustive) of potential adverse events, device related, procedure related and/or subject condition related.

-Next Page-

Table 3: List of foreseeable adverse events and anticipated adverse device effects

Air embolism	Interruption of desired pacemaker function due to electrical interference, either electromyogenic or electromagnetic
Angina pectoris	Keloid formation
Arterial puncture	Loss of normal device function due to battery failure or component malfunction
Bladder puncture	Muscle and nerve stimulation
Blunted or poor sensor response	Myocardial damage
Body rejection phenomena	Myocardial infarction
Bowel penetration	Myocardial irritability
Cardiac arrhythmias	Oversensing
Cardiac dissection	Pacemaker syndrome
Cardiac perforation	Palpitations
Cardiac tamponade	Pericardial effusion
Chronic nerve damage	Pericardial rub
Damage to vessels	Pericarditis
Device dislodgment	Phrenic nerve/diaphragm muscle stimulation
Dizziness	Premature battery depletion
	Programmer/software anomaly
Dyspnea	Pseudoaneurysm formation
Embolism	Psoas abscess
Endocarditis	
Excessive Bleeding	Septic arthritis
Exit block	Seroma
Failure to capture/loss of capture	Syncope
Femoral nerve injury with resulting paresthesias	Threshold elevation
Fluid accumulation	Thromboemboli
Hematoma formation, including retroperitoneal hematoma/hemorrhage	Thrombosis
High impedance	Undersensing
Inability to interrogate or program due to programmer or device malfunction	Valve damage
Induced ventricular ectopy or arrhythmias	Venous occlusion
Infection, local at access site, or system	Venous perforation
Insufficient cardiac output	Ventricular ectopy
Intermittent capture	Ventricular tachycardia

